The initial treatment of Patients with Functional constipation is based on fiber. There are multiple fiber products in the market, which are Promoted as a supplement for constipation without any scientific evidence to support ITS use. Furthermore, the tolerability of These compounds limits long-term Their use in esta patient population. Scientific evidence is required to support the effectiveness in the use of These fiber supplements in Patients With functional constipation.

6. Justification

There are multiple fibers are in the market That Promoted as a beneficial supplement for Patients With constipation, DESPITE esta, there is not enough scientific evidence derived from randomized and controlled studies to support ITS use. THEREFORE, it is Necessary to Provide evidence to support the use of blue agave fructans Tequilana Weber in Patients With functional constipation.

7A. hypothesis

Defined as a verifiable statement About the relationship Between a variable-dependent and an independent variable. (Remember That the concepts of "null hypothesis", "alternate hypothesis" are related to the statistical analysis So They Should not be included in this item)

General Hypothesis:

Plantago Psyllium When Compared With, the blue agave fructans Weber Tequilana have a like effect or are more effective in Improving functional constipation in adult patients.

Objectives

PRIMARY

1. To Evaluate the efficacy of the blue agave fructans Tequilana Weber in Patients With functional constipation.

SECONDARY

1. To compare the efficacy and tolerability of 5 and 10g doses of blue agave fructans Tequilana Weber in Patients With functional constipation.
2. To Evaluate the impact of the consumption of blue agave fructans Tequilana Weber on the quality of life of the subjects WHO ingest it by Applying the quality of life questionnaire SF-36.
3. To determine the impact of the blue agave fructans of Weber Tequilana intake in the fasting glucose, glycosylated hemoglobin A1c and the lipid profile (metabolic profile) of the subjects WHO ingest it.
4. To Evaluate the presence of short chain fatty acids (butyrate) before vs after the treatment with blue agave fructans Tequilana Weber.
5. To determine the impact of the ingestion of blue agave fructans Tequilana Weber in the microbiota before vs after ingestion.
6. Evaluate to the tolerance to the ingestion of blue agave fructans Weber Tequilana through the use of breath test.

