effects on intestinal transit Have Been observed from the first week of intake, in fact this is one of the Reasons to focus the study on functional constipation and intestinal transit.

Breath test:

A breath test will be Carried out in order to measure hydrogen and methane Concentrations previousle Exhaled In Patients randomized in visits 1 and 5.

In order to carry out the breath test gas chromatography equipment will be used, brand Quintron Breath Tracker.

For That, The Patients will be Asked:

- Not to take antibiotics prior weeks At least to the test.
- Stop the intake of food rich in fibers and starches 24 h before the test.
- Not to take alcohol, or smoke
- Have a minimum of 8 hours fasting
- Perform oral hygiene before starting the test and during the performance of measurements.

This test lasts 3 hours, during which the patient can not leave the laboratory facilities motility, can not speak too much or sleep. Exhaled air samples are taken every 15 minutes during this period.

SmartPill®:

[figure not shown]
SmartPill® test will be conducted on visits 2 and 4.

colonoscopy:

Colonoscopy study is a tool which will be subject to scrutiny patients ≥ 55 years with newly diagnosed constipation or those where changes in bowel habits observed in this age group. This fundamental objective, rule out potentially serious diseases and not to delay the diagnosis of these during the research study. one colonoscopic study all patients who have constipation and any of the following characteristics will be used:

1. Diagnosis of constipation less than 1 year
2. Subjects ≥ 55 years who do not have colonoscopic evaluation in the last 3 years prior to study entry
3. Chronic but with alarm data (: Unexplained weight loss, recent transrectal bleeding < 6 months, recent changes in the defecation pattern example) Constipation

Study Flow Chart

Patients include:

Studies with fiber supplements (Psyllium, Plums⁸) Have included 25 to 30 patients per group to find differences between groups.

In total it is planned to include 60 patients randomized as follows: 15 patients receive fructans blue agave Tequilana Weber dose of 5 g, 15 patients received the dose of 10 g, 15 patients received the dose of 5g of agave fructans blue Tequilana Weber + 10 g excipient and 15 patients received 15 g plantago psyllium.

9. Methodology Selection Criteria

a) Inclusion criteria (consider not participating in other research and contraception if necessary)

- Patients over 18 years old.

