The sample size was calculated from the formula mean differences for non-inferiority studies and data from 52 studies were used Holscher HD., Et a38, Erdogan A., et al 53 and R Closa-Monasterolo , et al 54. accuracy of 95% (0.05 probability of making an error or type I was used α) And a force or power of 80% (0.20 probability of committing a type II error or β).

$$n = \lambda/\Delta.$$

Where:

n = sample size

$$\lambda = 10.91$$

$$\Delta = 1$$

Where:

$$\Delta = \frac{1}{(\sqrt{\sum \sigma^2})} (\sum \sigma)$$

$$\sigma_1 = 0.01$$

$$\sigma_2 = 0.12$$

$$\sigma_3 = 0.43$$

$$\sigma_4 = 0.27$$

$$= \Delta \frac{1}{(0.82)} (0.82) = 1$$

$$= 10.91 \approx 11 n = 10.91/1$$

Taking a 20% loss during the study sample size are:

$$n = 13 \approx 15$$

d) Statistical significance

It is considered each of the variables under study as the statistically significant with a value of $p < 0.05$

e) Statistical analysis of the population

The study population are volunteers with functional constipation and statistically analyzed considering the per protocol population and intent-to treat.

f) statistical treatment

It does not, in our strategy of statistical analysis a power of 80% for our study with an alpha of 0.05 is contemplated to demonstrate non-inferiority. Therefore, a greater percentage of losses accepted 20% to give validity to our study.

11. List of materials to use resources.

Team	Model	Description
portable stadiometer	Seca213	Measuring range 20-205 cm Division 1 mm Brand: Seca
Impedance	RJLQIV	Impedance Analyzer Brand: RJL Systems Includes: analyzer, charger case, LEMO cables, resistor, 400 electrodes, software
Weighing machine	BBZ-420	Maximum capacity up to 140 Kg minimum division 100 g Zamac bar with matt chrome Pylons cursors zamac beige or white enameled Base 54 x 20 x 10.5 cm Scale weight: 17 kg authorization NOM Made from sheet metal Finished in baked enamel paint

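### The 0.05 error level for the non-inferiority claim is not tied to any decision rule across the three agave arms: if any one arm suffices, the chance of a false claim is about 6% to 12% at one visit

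*Combined protocol and SAP*

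**What the plan says.** - **Error level.** Section 10, Data analysis, item c) specifies an "accuracy of 95% (0.05 probability of making an error or type I was used" for α, with 80% power, in a formula for non-inferiority studies. Item f) repeats it: "alpha of 0.05 is contemplated to demonstrate non-inferiority". Item d) counts "each of the variables under study as the statistically significant with a value of" p < 0.05. Sidedness is not given.
- **Arms.** Section 8 (Patients include) allocates 60 patients equally: "15 patients receive fructans blue agave Tequilana Weber dose of 5 g, 15 patients received the dose of 10 g", 15 to 5 g agave plus 10 g excipient, and 15 to psyllium.
- **Hypothesis.** Section 7A: "Plantago Psyllium When Compared With, the blue agave fructans Weber Tequilana have a like effect or are more effective". It does not say which agave arm, or how many, must succeed.
- **Tests.** Item a) gives ANOVA or Kruskal-Wallis for continuous variables between groups, plus ANCOVA for covariates. It names no agave-versus-psyllium comparison. Item b) explains the non-inferiority aim but gives no margin.
- **Outcome.** Section 10 names one main outcome, a gain of at least one complete spontaneous evacuation over baseline, and lists the secondary variables separately. The main outcome has no time point. Under section 8 the evacuation diary is reviewed at Visit 4 (about one month), at Visit 5 (end of treatment) and again one month after stopping.

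**The concern.** Non-inferiority is a statement about a particular arm against psyllium. A significant omnibus test says only that some arms differ, and a non-significant one does not show similarity. Any non-inferiority claim must therefore come from arm-versus-psyllium comparisons that the plan neither names nor orders.

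There are three such comparisons and one general hypothesis. A favourable result in one arm could be reported as support for agave fructans while the other two failed, and nothing in the plan rules this out. The stated 5% would then hold for each comparison but not for the conclusion. Leaving the visit open adds a second choice that could be made after the data are seen.

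**Working it through.** **1. The plan's own figure.** Item c): n = λ/Δ = 10.91/1 = 10.91, rounded to 11. With 20% loss, 10.91 × 1.2 = 13.1, which the plan rounds to 13 and then 15; 4 × 15 = 60. The arithmetic reproduces.

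**2. What λ belongs to.** The noncentrality for an omnibus test of four groups (3 df, α = 0.05, power 80%) is 10.90, which matches 10.91. Two-arm constants 2(z_α + z_β)² do not match:
- one-sided 0.05: 2(1.645 + 0.842)² = 12.37
- one-sided 0.025: 2(1.960 + 0.842)² = 15.70

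The 5% in the sample size thus fits an omnibus test of difference, not arm-versus-psyllium comparisons.

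**3. Error over three comparisons at one visit.** Inputs from the documents: three agave arms, one shared psyllium arm, equal n. Assumptions: a normally distributed outcome, all three arms exactly at the null boundary, and success in any arm counts.

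The shared control gives each pair of test statistics the correlation (σ²/n) / (2σ²/n) = 0.5. The chance of at least one false claim is 1 − Φ₃(z, z, z; ρ = 0.5):

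| Level per comparison | z | Formula | Simulated t-tests, n = 15 | If independent |
|---|---|---|---|---|
| one-sided 0.05 | 1.645 | 11.8% | 11.7% | 1 − 0.95³ = 14.3% |
| one-sided 0.025 (two-sided 95% interval) | 1.960 | 6.3% | 6.3% | 1 − 0.975³ = 7.3% |

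With n = 12 per arm the simulated values are 11.9% and 6.3%.

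**4. Other assumptions, one visit, one-sided 0.05 each.**
- Two arms at the boundary and the third clearly non-inferior: 8.8%.
- One arm at the boundary: 5%.
- One designated or one pooled comparison: 5%.
- All three arms must succeed, all at the boundary: 0.5%.

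**5. If a result at either Visit 4 or Visit 5 could count.** For an assumed between-visit correlation from 0.9 down to 0.3, the chance is 16% to 21% at one-sided 0.05 each and 9% to 12% at one-sided 0.025 each. The documents give no correlation.

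**6. ANOVA as a gate.** If pairwise tests of difference follow only a significant ANOVA (n = 15 per arm), the false-positive rate is 4.1% when all arms are equal and 9.0% when one agave arm truly differs. These rates concern tests of difference and say nothing about non-inferiority claims.

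**The case against.** The strongest reply is that the plan never says it will run three unadjusted comparisons. Its between-group test is omnibus, its λ is the omnibus constant, and neither sidedness nor a margin is printed. This stands. A reader might infer that the trial's error rate simply is 12%, or more than double the stated level. The documents do not support that: 12% needs one-sided 0.05 per comparison, an any-arm rule and all three arms at the boundary. Read from two-sided 95% intervals, the figure is 6.3%, only modestly above 0.05. The reply does not rescue the plan, because the omnibus test cannot deliver the aim in item b).

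The any-arm rule is also not written down; section 7A could equally mean all arms or a pooled comparison. This stands too, and it makes the missing success rule the core of the point.

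Two other strong readings fail. One is that the plan has no hierarchy and every variable can carry the agave claim. Section 10 separates one main outcome from the secondary variables, and the figures above include nothing for testing those. The other is that success at either visit counts. No section says so; the time point is simply absent.

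Finally, the main outcome may be meant as a responder criterion, whereas the calculation uses a normal outcome. With 15 per arm, a test on proportions could have a somewhat different actual level. The figures are approximations on this account.

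**Conclusion.** The concern holds as a gap in the decision rule. The plan attaches 0.05 to a non-inferiority conclusion without saying which agave comparison, how many arms, which visit or which side the level refers to, and its only named between-group method cannot support that conclusion. The size is conditional: about 6% to 12% at one visit under the any-arm rule with all arms at the boundary, lower if fewer arms are at the boundary or more arms must succeed, and higher only if either on-treatment visit were allowed to count. It applies to the main outcome alone. The missing margin is a separate gap, but the level cannot be given meaning without one.

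**What to change.** In section 10, Data analysis, item d), state that:

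1. the 5% level, with its sidedness, applies to the three agave-versus-psyllium comparisons on the main outcome at one named visit;
2. each comparison is judged by a confidence interval against a margin stated in advance;
3. the comparisons are tested in a fixed order set by the sponsor before unblinding (as the trial is single blind, before anyone involved sees outcomes by arm), each at the full level, stopping at the first failure;
4. all other variables and visits are exploratory and reported with confidence intervals.

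Stopping at the first failure holds the chance of any false claim at the stated level, because no later claim can follow a failed comparison. The order adds no patients. By contrast, holding one-sided 5% by Dunnett (about 0.0196 per comparison) or Bonferroni (0.05/3 = 0.0167) would multiply n per arm by about 1.36 or 1.43 at 80% power; for Bonferroni, ((2.128 + 0.842)/(1.645 + 0.842))² = 1.43.

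The cost is that an arm later in the order cannot be claimed if an earlier one fails, whatever its own result. The sponsor must also settle the margin and sidedness, so this is more than a change of one sentence.

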7. To evaluate- gastrointestinal transit in Patients With functional constipation and after ingestion of before blue agave Tequilana Weber fructans.

8. Methodology: General Design.

Describes the overall design of the study and, if relevant, specify the following points:

- a) Study design: Describes if it is randomized / non-randomized, controlled, cohort, Blinding type (double-blind, single), type of controls (placebo, active medication), wash period.
- b) Maneuver or intervention description.
- c) Sample size (# of Patients to be included; justify the calculation)
- d) Treatment allocation mechanism (random / open)
- e) Treatment groups and
- f) Duration of Individual follow-up

Study Design

This is a prospective, randomized, controlled and single blind study to determine the phase III efficacy of the blue agave fructans Tequilana Weber intake in subjects with functional constipation.

In order to Achieve so, it is planned to include over 18 years of Patients age Fulfill the WHO as well as inclusion criteria The Rome III criteria for functional constipation. (See table below) 2.

The phase of our study is designated based on article 66 of chapter II "On Pharmacological Research" of the Regulation of the General Law on Health in Research That defines PHASE III studies Follows as: It is the administration of a research drug to large groups of Patients (Usually external), to define ITS therapeutic utility and identification identify adverse reactions, interactions and external factors That May alter the pharmacological effect.

ROME III criteria

To Comply with the presence of symptoms for more than 6 months before diagnosis, Having Said symptoms for at Least 3 consecutive months or not, and:

1. Absence of abdominal pain or discomfort in the last 3 months.
2. Include 2 or more of the following symptoms.
 - Excessive effort in more than 25% of the evacuations.
 - Hard stool or "pellets" in more than 25% of evacuations.
 - Sensation of incomplete evacuation 25% of evacuations.
 - Sensation of blockage or blockage in 25% evacuations.
 - Maneuvers to Facilitate expulsion in 25% of evacuations.
 - Less than 3 evacuations per week.
3. Stool consistency decrease, rarely, without the use of laxatives.
4. Insufficient criteria of IBS.

Patients of the institute will be called after invitations to Participate in Placing a protocol for Patients With constipation. Patients Who Have Not Been registered and meet the inclusion criteria May Also Participate.

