The study to be Carried out will be Explained and read and, where appropriate, the informed consent will be signed by the Patient During the initial visit (Visit 1) of eligibility, Where the subject will be Given 2 questionnaires (see annexes), one They meet to determine if the ROME III criteria for functional constipation (FC) and another to ASSESS if the patient does not meet the criteria for irritable ROME III bowel syndrome (IBS) and a baseline breath test will be performed.

Having met the inclusion criteria, the patient will be EVALUATED by a graduate in nutrition with the objective of Evaluating the fiber intake in the subject's usual diet. The amount of daily fiber intake will be standardized and a diary will be Given to Evaluate Said intake (see annexes) as well as a diary Where the subject will keep a record of his / her evacuations (see annexes).

In Addition, the previous use of fiber supplements and laxatives, which must be suspended at Least 2 months prior to randomization, will be EVALUATED.

The subject will return to a second visit (Visit 2) (Which will depend on Whether the patient is taking laxatives or fiber supplements) for a complete physical evaluation and the fiber intake diary will be Assessed to determine the amount of fiber intake in the diet as well as the diary of evacuations and the SmartPill © will be Given and That way, the patient will return to the hospital to register the data after the capsule Having evacuated.

The patient will return a week later (Visit 3) on a 12 hour fast, the fiber intake and the evacuation diaries will be re-EVALUATED and will be EVALUATED They again by a nutritionist. A new breath test will be Carried out. The subject will be

Asked to complete the SF-36 Quality of Life Questionnaire. A stool sample will be Collected for ITS analysis in Addition to a blood sample for determination of fasting glucose, glycosylated hemoglobin A1c, Insulin and full lipid profile.

The subjects will be randomized to receive one of four treatments That can be Psyllium plantago 15g, blue agave Tequilana Weber fructans at doses of 5, 10g and blue agave Tequilana Weber fructans at a dose of 5 g + 10 g excipient for a concentration of 33 % of blue agave fructans Tequilana Weber.

The randomization will be computer-generated with a participation number and the assignment of the treatment will be consecutive.

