SmartPill	REF. 50100400	The capsule measured 26.8x11.7 mm and transmits a radio frequency at 434 MHz to an electronic device that uses the patient. The capsule has a helmet containing polyurethane sensors measuring luminal pH, pressure, temperature and a battery with minimum of 120 h. After activation, the pH is measured every 5 sec for the first 24 hours, every 10 seconds from 24 to 48 hours and every 2.5 min after 48 hours; pH changes are detected with a sensitivity of ± 0.5 pH units. Pressure is measured from 0 to 350 mmHg and collected every 5 seconds for the first 24 hours and every second thereafter, the accuracy with which pressures are measured are ± 5 mmHg for pressures below 100 mmHg and $\pm 10\%$ for pressures greater than 100 mmHg.
Headband	Seca201	Ergonomic measuring tape circumferences Brand: Seca
Food Replicas	WA29168HR	Pack food replica plate kit It Includes: 36 replications
Littmann stethoscope	Master Classic	Physical exploration
Software: NutriKcal	version 0	Analyzes the nutritional composition per serving recipes
Software: Statistical	SPSS version 20	Analysis of data
Software: Determination of fatty acids	GC / MSD Agilent Chemical Station	Determination of fatty acids with spectra library to search NISTC (National Standard Institute and Technology)
Gas chromatography coupled to mass detector	6890	Identification and quantification of fatty acids
PCR equipment	7500 Real Time Fast	Identification of bacteria Brand: Apple Brand BioSystems
Imperial incubator III	310 M	Incubator bacteria Brand: Lab-line
Auxiliary services	-----	The INCMNSZ has a laboratory in which corresponding studies of blood samples will be requested.
Emergency services	-----	INCMNSZ has the emergency room where participants will be referred research protocol if required by the intervention.

12. Risks and Benefits Study

- Discomfort generated by the study (when blood samples, record the total number of punctures, the amount of blood by puncture and / or total and the frequency of punctures.)
- Potential risks (presence of complications or side effects, drug interactions considered, considering psychological effects of evaluation methods, v.gr.: surveys sensitive subjects)
- Detection methods anticipated risks.

- d) Security measures for early diagnosis and prevention of risks.
- e) Procedures for resolving risks if they arise.
- f) Expected direct benefits.
- g) Expected indirect benefits.
- h) Overall weight of risks versus benefits of the proposed study.

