Discomforts generated by the study:

Discomfort from the study are related to the puncture for blood collection (3). It is anticipated that the fiber, when containing fructans, generate a fermentation process with flatulence and bloating. However, reports of studies using the fiber, have shown that this effect is transient lasting 2 weeks.

Risks:

Regulation of the General Law of Health in Research for Health, said that obtaining biological samples represents a minimal risk in the investigation. The risks of blood sampling are: possibility of slight bleeding or bruising at the puncture site, dizziness or fainting and rarely arterial puncture may occur. Personnel draw the blood sample is trained for this, which will minimize the risks of complications.

If there are complications will be referred directly to your treating physician. It is anticipated in the informed consent we do not have resources in case complications arise.

Benefits:

Administration fiber, it has shown to be healthy and beneficial for the treatment of functional constipation. Such supplementation, is the first line treatment of functional constipation. Patients entering this study will benefit from fiber start treatment within the diagnostic and therapeutic approach constipation.

Moreover, thanks to the participation of volunteers, your community can benefit significantly by finding new ways to address this medical complication.

Rescue measures:

If the patient has no spontaneous evacuation after 72h will prompt the patient to contact the research team, for instructions such as laxatives previously prescribed by your physician. If distended or flatulence, using anti detergents (simethicone) that is effective to treat this condition is allowed. For present colic, it can be used a conventional antispasmodic. each of the side effects will be recorded as well as the need for therapies rescues specified above.

13. Schedule of activities

The letter updating the research project is attached. (Annex 1)

Activities	2018												2019												2020											
	J	F	M	A	M	J	J	A	S	O	N	D	J	F	M	A	M	J	J	A	S	O	N	D	J	F	M	A	M	J	J	A	S	O	N	D
Moith																																				
Research topic selection	■																																			
Search and review of the biography	■	■	■	■	■	■	■	■	■	■	■	■	■	■	■	■	■	■	■	■	■	■	■													
Protocol writing	■	■																																		
Review of the protocol by the research group			■	■																																

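### Transit objective: some of the slowest capsule times can reflect a rescue laxative or the end of recording, and the plan has no rule for them

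*Combined protocol and SAP*

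**What the plan says.** Secondary objective 7 is gastrointestinal transit before and after agave fructans. Section 8 (General Design) states "SmartPill® test will be conducted on visits 2 and 4". Randomization is at Visit 3, so the first capsule is a pre-treatment measurement and the second falls about one month into treatment.

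- **End of a reading.** For Visit 2, section 8 says "the patient will return to the hospital to register the data after the capsule Having evacuated". It gives no maximum time and no rule for a capsule that has not come out. The next contact is stated as "The patient will return a week later (Visit 3) on a 12 hour fast". Section 11 (materials) gives the capsule "a battery with minimum of 120 h", so the guaranteed recording is shorter than that week.
- **Rescue.** Section 12 (Rescue measures) says "If the patient has no spontaneous evacuation after 72h will prompt the patient to contact the research team, for instructions such as laxatives". It adds "each of the side effects will be recorded as well as the need for therapies rescues specified above". It does not mention capsule days, or whether it applies before randomization.
- **Washout.** Section 8 requires fibre supplements and laxatives to be suspended at least 2 months before randomization. The Visit 2 capsule lies inside that period.
- **Analysis.** Section 10 does not list transit among the measured variables. Its analysis plan names a paired t-test or Mann-Whitney U within groups, and ANOVA or Kruskal-Wallis between groups. It has no rule for times after rescue or for capsules not passed.

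**The concern.** A capsule that leaves after a laxative gives an exit time that is not a transit time under the study fibre alone. A capsule still inside when recording stops has no exit time. Both events fall mainly on slow patients, where a fibre effect on transit would be looked for.

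For stools the plan deals with this: a spontaneous evacuation is defined as one without laxatives, suppositories or enemas. For transit there is no counterpart. If raw exit times go into the planned tests, the before-after contrast mixes fibre with rescue, and the direction of the error depends on whether rescue operates at one capsule visit or both. The documents leave that open.

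**Working it through.** **No plan figure to reproduce.** The documents give no transit mean, SD, effect or power. They say only that transit is slow in constipation. From the documents: 72 h (rescue trigger), 120 h (battery minimum), 15 patients per arm. Everything else below is assumed.

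**1. How common are gaps over 72 h?** With random (exponential) gaps, P(gap > 72 h) = exp(−72 / mean gap).
- 2 stools per week: mean gap 168/2 = 84 h, P = exp(−72/84) = 0.42.
- 3 per week: mean gap 168/3 = 56 h, P = exp(−72/56) = 0.28.

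**2. Lognormal model in which every capsule past 72 h is rescued.** Let T have median m and log-SD s. Assume a laxative exit 6 to 18 h after 72 h, so about K = 84 h. The mean time removed by rescue is

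C(m) = m·exp(s²/2)·Φ(d₂ + s) − K·Φ(d₂), with d₂ = ln(m/K)/s.

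For m = 60, s = 0.6: mean = 60·exp(0.18) = 71.83 h, d₂ = −0.561, and C = 71.83 × 0.5156 − 84 × 0.2875 = 12.9 h. This is the false shortening when rescue acts only at Visit 4 and the fibre does nothing.

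For a true 20% shortening, the mean change is 0.2 × 71.83 = 14.4 h. At m = 48, C = 57.46 × 0.3697 − 84 × 0.1755 = 6.5 h. With rescue at both visits the observed change is 14.4 − 12.9 + 6.5 = 8.0 h, an attenuation of about 44%.

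| Median, log-SD | Past 72 h | False shortening, Visit 4 only | True change | Observed, both visits | Attenuation |
|---|---|---|---|---|---|
| 50 h, 0.6 | 27% | 7.4 h | 12.0 h | 8.0 h | 33% |
| 60 h, 0.6 | 38% | 12.9 h | 14.4 h | 8.0 h | 44% |
| 72 h, 0.5 | 50% | 15.2 h | 16.3 h | 8.3 h | 49% |

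These three settings give the ranges quoted. The opposite corners of the same grid give 4.2 h and 23% (50 h, 0.5), and 21.2 h and 57% (72 h, 0.6). At 60 h and 0.6, 12% of capsules would pass 120 h. If only half of the capsules past 72 h are rescued, the false shortening is 6.5 h and the observed change about 11.2 h.

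**3. Model with explicit stool gaps.** Gamma gaps (shape 3), log-SD 0.6, exit with the first stool after the latent transit time, laxative stool 12 h after the trigger. The paired values are for latent medians of 48 and 72 h.

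| Stools per week | Rescue before exit | True change → observed, rescue at both visits | False shortening, Visit 4 only |
|---|---|---|---|
| 2 | 64%, 72% | 10.8 → 5.3 h; 16.8 → 6.3 h | 38.6, 55.4 h |
| 3 | 35%, 41% | 10.9 → 8.9 h; 17.1 → 11.5 h | 13.0, 22.3 h |
| 5 | 6%, 7% | 11.4 → 11.2 h; 17.2 → 16.4 h | 1.2, 2.6 h |

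**4. False positives at n = 15** (median 60 h, log-SD 0.6, visit correlation 0.6, no fibre effect, rescue only at Visit 4). The paired t-test rejects in about 14% of trials at the nominal 5%, and so does a signed-rank test on raw exit times. Tying all times above 72 h as slowest at both visits brings this back to 4 to 5%. Ranking only the rescued Visit 4 capsules as slowest, while long Visit 2 times keep their values, gives about 15% in the opposite direction.

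**The case against.** Four objections have force.

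- **Rescue follows absent stools, not a retained capsule.** A reader might infer that the slowest times simply are laxative or battery artefacts. The documents do not support that. A patient can pass stools without the capsule and have a clean time above 72 h. Rescue goes through the research team, laxatives are one possible instruction, and 120 h is a floor rather than a cut-off. What stands is that slow times can be affected.
- **Long gaps are not shown to be usual.** "Less than 3 evacuations per week" is one of six symptoms, of which two are needed, and the shares in step 1 are minorities.
- **Rescue is not unrecorded.** The need for rescue is noted, and evacuation diaries are kept. What is missing is the laxative time relative to the capsule and any use of it in the analysis.
- **Means overstate the effect on inference.** In the lognormal model the visit medians do not move, and paired t-test power at n = 15 is 0.26 without rescue against 0.28 with rescue at both visits. The attenuation is therefore in hours, not in detection. The case of rescue only at Visit 4 survives: the median within-patient change moves by 5.4 h and false positives rise.

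A reader might also infer that shrinkage favours the hypothesis of a like effect to psyllium. That does not follow. The hypothesis concerns improvement of constipation, the main outcome is complete spontaneous evacuations, and no non-inferiority test of transit is planned. The two rescue scenarios also bias in opposite directions.

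**Conclusion.** The point holds in limited form. The transit comparison has no rule for times affected by rescue or for capsules not passed before recording ends, and the washout and rescue statements leave open whether rescue can act at Visit 2. Comparing raw exit times can therefore give a wrong before-after result: a false shortening if rescue acts only at Visit 4, a compressed mean change if it acts at both visits. No net direction is established.

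The size is unknown. About 7 to 15 h of false shortening and 33 to 49% attenuation hold for the three assumed settings. Counting every capsule past 72 h as rescued is the most rescue of such capsules that the model allows, so the figures are upper limits in that respect only. They do not bound other models: with stool gaps the false shortening runs from about 1 h at 5 stools per week to 55 h at 2. The 72 h clock can also start before the capsule is swallowed, so shorter times can be affected too.

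This concerns one secondary objective. It should be settled before capsules are given, because laxative timing not captured then may be unrecoverable.

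**What to change.** Leave the rescue rule unchanged.

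1. Reconcile the washout statement in section 8 with the rescue statement in section 12, so that it is clear whether rescue applies while the Visit 2 capsule is in place.
2. Define the transit variable in section 10.
3. At both visits, record the time of any laxative taken while a capsule is in place, and whether the capsule exited before recording ended.
4. Rank rescue-affected and unexited capsules together as slowest, using the same condition at Visits 2 and 4. If rescue turns out not to operate at Visit 2, define the tied group by something observable at both visits, such as the diary showing that the 72 h trigger was reached before exit, whether or not a laxative was taken.
5. Use a paired rank-based method within arms (Mann-Whitney U is not paired) and a rank-based method between arms.
6. Keep censored-time analysis as a sensitivity analysis only. Censoring at rescue is informative, because rescue goes to patients who are not evacuating.
7. Report counts of rescue and non-exit by arm and visit.

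The cost is a small addition to the capsule form, one paragraph in the analysis plan, and some loss of precision from tied slow values.
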